A randomized control trial of furosemide or placebo with usual antihypertensives in the antepartum management of severe hypertension with wide pulse pressure Protocol Number I Version 2 02/21/20

Principal Investigator: [name] [name], MPH, MCR

Sub-Investigator: [name]

Research Site: Kapi'olani Medical Center for Women and Children [name] [contact]

Version 2

Protocol Number I

Protocol Title: A randomized control trial of furosemide or placebo with usual antihypertensives in the antepartum management of severe hypertension with wide pulse pressure

Version Date: 2/21/20 Protocol Number: I

Principal Investigator: [name] [name]

Sub-Investigator(s): [name]

Research Site(s): Kapiolani Medical Center for Women and Children

Section I: Purpose and Background

1. Purpose

Primary objective: To determine whether the addition of intravenous furosemide with usual antihypertensives is associated with a reduction in mean systolic blood pressure from baseline compared to treatment with placebo plus usual antihypertensives (intravenous labetalol, intravenous hydralazine, or oral immediate release nifedipine) for the management of severe antepartum hypertension.

Secondary objectives:

To determine whether the addition of intravenous furosemide with usual antihypertensives is associated with a reduction in mean diastolic blood pressure compared to treatment with placebo plus usual antihypertensives listed above.

2. Background

Introduce and provide support for the research being proposed. Basic information relevant to the context of the research question and study design should be included in this section. Additionally, this section should be written in a way that a person who is not an expert in the field can understand.

Blood pressure is a measure of blood flow and resistance in blood vessels. In normal pregnancy, total blood volume increases while systemic vascular resistance decreases, thereby leading to an overall reduction in blood pressure with return to baseline at term. Hypertensive disorders in pregnancy, including preeclampsia, are a polymorphic syndrome characterized by elevated blood pressures which can affect multiple organ systems¹. Although the exact mechanism of preeclampsia has yet to be determined, previous studies have shown that there may be two distinct phenotypes – one characterized by vasoconstriction and diminished micro-circulation and the other involving a hyperdynamic high cardiac output state^{2,3}.

Given its potential for both significant maternal and fetal morbidity, hypertensive disorders in pregnancy comprise a substantial proportion of antepartum admissions. Management of acute severe hypertension (systolic BP≥ 160 or diastolic BP≥ 110) is important to reduce the risk of stroke, hypertensive encephalopathy, placental abruption, and heart failure or myocardial infarction⁴. In the antepartum and intrapartum period, the use of antihypertensives including labetalol, nifedipine, and hydralazine have been well-described⁴. Despite these options for blood pressure control, preeclampsia can be a progressive disorder that may not respond to the aforementioned agents.

Version 2 Protocol Number I

In preeclampsia manifested by high blood volume due to salt and water retention rather than vasoconstriction, standard antihypertensives may be less effective. Furosemide is a commonly used diuretic that can lower blood pressure by inhibiting the absorption of sodium, chloride, and water, thereby decreasing the volume of blood that the heart pumps. The onset of action of action of IV furosemide is 5 minutes, with peak effect at 30 minutes, and duration of action of 2 hours⁵.

Previous studies have demonstrated the safety and efficacy of furosemide to treat preeclampsia in the antepartum and postpartum period as well as its utility in treating heart failure in pregnant women^{6,7}. To our knowledge, no randomized studies exist that investigate the use of furosemide in treating hypertension in the antepartum period. We aim to determine the utility of the addition of furosemide to usual antihypertensives in this clinical setting.

References

3. Inclusion criteria

Define subject eligibility based on scientific rationale and safety considerations. Include the timeframe of data collection for retrospective studies.

Inclusion Criteria

- Subjects 18 years of age or older
- Subjects with intrauterine pregnancy at or beyond 20 weeks of gestation
- Subjects with a diagnosis of hypertensive disorder in pregnancy
- Subjects with persistent (on repeat BP check 15 min apart) severe range blood pressure recordings (systolic BP≥ 160 or diastolic BP≥ 110) with wide pulse pressure (>60 mmHg)
- Subject able to provide informed consent

4. Exclusion criteria

Define exclusion criteria to limit the study population and prevent subjects from being exposed to excess risk by the study. Exclusion criteria should account for warnings, precautions, and contraindications listed in current product labeling.

Exclusion Criteria

- Subjects less than 18 years of age
- Subjects with intrauterine pregnancy less than 20 weeks of gestation
- Subjects with known fetal anomaly
- Subjects with hypokalemia (K <3.0 mEg/L) on admission

Version 2

Protocol Number I

- Subjects with anuria (<50mL urine in 24 hours) or renal failure
- Subjects previously taking diuretics or potassium supplements for any reason
- Subjects with a known allergy/adverse reaction to furosemide
- Subjects who are unable to understand and/or sign the informed consent
- Active labor (≥ 6cm dilated) or epidural in place

5. Vulnerable subjects

Provide justification for the necessary inclusion of vulnerable populations. Vulnerable subjects often need additional protection and certain restrictions and requirements may apply. Children, pregnant women, and prisoner are examples of vulnerable populations.

Preeclampsia exclusively affects pregnant individuals. As such, pregnant subjects should be studied. To protect these patients, consent forms will be collected and we will reiterate that declining study participation will in no way affect the quality of care they will receive.

Section III: Methods and Procedures

1. Methods and procedures

Summarize the research design (observational, randomized, case-study, etc.) and include a schematic diagram if applicable. Provide a sequential list identifying all the procedures of the study, distinguishing between experimental procedures and procedures resulting from routine care. Explain procedures, situations, or materials that may be hazardous and subsequent precautions to reduce subject risk.

This will be a prospective double-blinded randomized placebo control trial of women ≥20 weeks of gestation with persistent antepartum hypertension (sustained SBP ≥160 or DBP ≥110 mmHg) and a wide pulse pressure (>60 mmHg) who meet all inclusion criteria and have no exclusion criteria. It is routine that laboratory studies are performed on admission for all women with hypertensive disorders. If electrolyte disturbances exist, therapy will not be initiated unless the electrolyte is normalized or repleted.

After informed consent and upon meeting inclusion criteria with severe range hypertension with wide pulse pressure, the study personnel will inform pharmacy personnel who will then randomly assigned the patient to groups by opening the next previously prepared sequential and numbered opaque study envelope. Participants will be randomized to furosemide plus an antihypertensive versus placebo containing normal saline and an antihypertensive. The pharmacy staff will send the assigned treatment. which will be administered by the bedside nurse. The vials containing the treatment will be indistinguishable as both furosemide and normal saline placebo are clear, colorless solutions. Thus, the provider, nurse, and patient will be blinded to the treatment. The choice of antihypertensive will be determined by the primary OB provider. At our institution, this will be one or more of the recommended medications for urgent blood pressure control as outlined by the American College of Obstetricians and Gynecologists Practice Bulletin on gestational hypertension and preeclampsia. These include IV labetalol, IV hydralazine, or immediate-release oral nifedipine. As meta-analyses have not shown that one of the aforementioned antihypertensives is superior than another, and all are reasonable options, the choice of antihypertensive will be left up to the OB

Version 2

Protocol Number I

provider^{8,9}. This will also improve the generalizability of the study as it does not interfere with what is typically done in clinical practice.

As a procedure of the study, patients will have their blood pressure recorded at least every 15 minutes up to one hour after administration of the study drug. Thereafter, as part of routine care, patients in both groups will receive similar antepartum surveillance, including blood pressure and pulse assessment every four hours or more frequently if vital signs are abnormal, daily weight measurement, and daily urinary output measurements.

Study Procedures

- 1. Antepartum patient diagnosed with a hypertensive disorder in pregnancy.
- 2. Patient approached for study participation and informed consent obtained if interested.
- 3. Patient develops severe range BP (SBP>160 and/or DBP>110) with increased pulse pressure (>60mmHg). This will be considered baseline BP.
- 4. When ordering provider's choice of antihypertensive, pharmacy notified that patient is study participant and randomizes patient by choosing from sequential opaque envelope.
- 5. a. Patient randomized to treatment arm and receives 40mg /4mL IV furosemide in addition to usual antihypertensive.
 - b. Patient randomized to placebo and receives 4mL normal saline in addition to usual antihypertensive.
- 6. Blood pressure check every 15 minutes after administration of furosemide/placebo for four recordings (15, 30, 45, 60 minutes)

2. Data analysis

Specify statistical and analytical methods (statistical power, sample size, significance level, etc.).

The primary outcome variable is reduction in mean systolic BP during the 1-hour period after drug administration. BP will be taken every 15 minutes for 1 hour and averaged. Intention-to-treat analysis will be performed. This study will use a two-sided t-test with the null hypothesis set at the standard significance level (p –value < 0.05), to determine if the addition of furosemide to usual antihypertensive significantly reduces blood pressure.

Change in average BP from baseline will be tested comparing the group receiving furosemide and the group receiving placebo using Mann-Whitney U, as BP usually presents as a non-parametric continuous variable. Multivariate regression will be used to adjust for potential confounders, such as maternal age, BMI, diabetes, baseline BP, antihypertensive chosen by the primary obstetrician, number of doses of antihypertensive, and gestational age. Comparative testing will be done to explore differences between the furosemide and placebo groups. Continuous variables satisfying the assumption of normality will be tested using the Student t-test and means and standard deviations will be reported. Otherwise, variables will be tested using the Mann-Whitney U test and will be reported using medians and interguartile ranges. The x2 or

Version 2

Protocol Number I

Fisher exact test will be utilized to test categorical variables and sample sizes and percentages will be reported.

A power calculation was completed using OpenEpi, Version 3, open source calculator—SSMean. The assumption of normality and that both groups will have the same common variance was applied. We set the standard deviation value as 20mmHg in the power calculation, which is based on pilot data from our own practice as well as data found in a randomized clinical trial using furosemide versus placebo (Ascarelli et al, Ob/Gyn 2005). A 15mmHg reduction in mean systolic blood pressure in the placebo group compared with the IV furosemide group was considered to be clinically significant as this represents an attainable, yet safe reduction from severe to mild range blood pressure. Using the 2-group Student t-test of equal means, 28 patients per study arm for a total of 56 patients would be required to detect a difference of 15mmHg with 80% power and a significance level of p=0.05. Once data has been collected, we will test for normality and use the appropriate statistical tests.

To account for patients who withdraw from the study or who need to be excluded after consent, 35 per arm or 70 total patients are to be enrolled. A randomization schedule will be created using block randomization with 10 blocks of 10 participants allocating randomization numbers to drug or placebo. The numbers will be sequentially assigned to participants by the pharmacist on duty. The hospital pharmacy will maintain the master list of the randomization log with patient study identifiers.

Data monitoring

Describe data monitoring methods for studies with more than minimal risk (i.e. data monitoring committee). Explain adverse event reporting procedures.

This is a greater than minimal risk study. Adverse events will be reported to the sub-investigator and primary investigator by the nurse and/or the obstetric provider. Furthermore, the sub-investigator will be actively following study participants closely to monitor for adverse events. If found, these will be reported to the institutional review board according to their reporting polices.

3. Data storage, security, and confidentiality

Describe where data will be stored and how data will be secured during the study. Provide information on confidentiality measures (coding, storage mechanisms, etc.). Indicate who will have access to the data and how the data will be used. If subject identifiers will be released, describe to whom and for what purpose the data will be released.

Data will be stored on a password-protected computer and maintained for 10 years after study completion. The data will be recorded in Microsoft Excel and will only be transmitted electronically through UCERA's encrypted email service among other study personnel in the same encrypted network. Access to subject data will be limited to the principal investigator, sub-investigators, and study staff. Data will be de-identified when data collection is complete, at which time each subject will be given a subject ID number. A key containing subject ID numbers will be maintained by the investigator and sub-investigator. Data will only be used for research purposes.

Version 2

Protocol Number I

4. Data Sharing

Describe plans for data sharing, particularly for publication purposes. Many journals now require authors to disclose how de-identified individual level data will be shared. Some journals require data sharing plans to be posted in a public registry, such as Clinicaltrials.gov. Additional information about data sharing can be found here:

https://grants.nih.gov/grants/sharing_key_elements_data_sharing_plan.pdf https://grants.nih.gov/grants/policy/data_sharing/data_sharing_workbook.pdf

The following statements are in response to data sharing guidelines by Elsevier.

Will individual participant data be available (including data dictionaries)? Individual participant data will be made available.

What data in particular will be shared?

Individual participant data that underlie the results reported any future manuscript, after deidentification (text, tables, figures, and appendices).

What other documents will be available?

There are no plans for additional documents to be made available.

When will data be available (start and end dates)?

Beginning 9 months and ending 36 months following any publication.

With whom?

Researchers who provide a methodologically sound proposal.

For what types of analyses?

To achieve aims in the approved proposal.

By what mechanism will data be made available?

The data will be deposited to Mendeley Data, a data repository that is supported by Elsevier and the American Journal of Obstetrics & Gynecology.

5. Transition from research participation (if applicable)

Describe how subjects who terminate participation will be transitioned to regular care (such as, taper study medication, return to primary care provider).

Subjects who terminate participation will resume regular care as determined by her primary treatment team. The investigators will discontinue collecting data on the individual and the choice of medications for acute blood pressure control will no longer be influenced by the investigators or study protocol.

Section IV: Risk/Benefit Assessment

1. Risk category (Contact HPHRI if you need assistance determining risk level)
State the risk of participating in the study as either Minimal or Greater than
Minimal. Risk is defined as the potential harm associated with the research that a

Version 2

Protocol Number I

reasonable person would find injurious. Minimal Risk means that the probability or magnitude of harm or discomfort anticipated in the research are not greater than those ordinarily encountered in daily life or during the performance of routine physical or psychological examinations or tests.

Participation in this study presents greater than minimal risk to subjects but not greater than the risks incurred by their existing disease process. As patients admitted with severe preeclampsia are required to have intravenous access, no additional invasive lines would be placed for the sole purpose of administering the study medications. Additionally, furosemide is already used for the aforementioned indication (severe range blood pressure with wide pulse pressure) in pregnant women. As furosemide is an approved drug being used for its approved indication in this study (ACC/AHA [Whelton 2017], risks incurred to the patient are outweighed by the potential benefit of treating a life-threatening condition (severe range blood pressure).

2. Potential risk(s)

Describe any potential risks associated with the study (physical, psychological, sociological, economic, and/or legal). If possible, estimate the probability of a given risk and potential reversibility.

Potential risks associated with participation in this study include the known pharmacologic effect of furosemide, which include fluid/electrolyte loss as well as rare side effects such as.

Cardiovascular: Necrotizing angiitis, orthostatic hypotension, thrombophlebitis, vasculitis Central nervous system: Dizziness, headache, paresthesia, restlessness, vertigo Dermatologic: Acute generalized exanthematous pustulosis, bullous pemphigoid, erythema multiforme, exfoliative dermatitis, pruritus, skin photosensitivity, skin rash, Stevens-Johnson syndrome, toxic epidermal necrolysis, urticaria

Endocrine & metabolic: Glycosuria, hyperglycemia, hyperuricemia, increased serum cholesterol, increased serum triglycerides

Gastrointestinal: Abdominal cramps, anorexia, constipation, diarrhea, gastric irritation, mouth irritation, nausea, pancreatitis, vomiting

Genitourinary: Bladder spasm

Hematologic & oncologic: Agranulocytosis, anemia, aplastic anemia, eosinophilia, hemolytic anemia, leukopenia, purpura, thrombocytopenia

Hepatic: Hepatic encephalopathy, intrahepatic cholestatic jaundice, liver enzymes increased

Hypersensitivity: Anaphylaxis, anaphylactoid reaction, anaphylactic shock

Immunologic: DRESS syndrome

Neuromuscular & skeletal: Muscle spasm, weakness

Ophthalmic: Blurred vision, xanthopsia

Otic: Deafness, tinnitus

Renal: Interstitial nephritis (allergic), renal disease

Miscellaneous: Fever

Source: https://www.uptodate.com/contents/furosemide-drug information?search=furosemide&source=panel_search_result&selectedTitle=1~148&usa ge type=panel&kp tab=drug general&display rank=1

Version 2

Protocol Number I

3. Protection against risk(s)

Describe how the study will minimize or prevent any potential risks. Techniques to minimize risk include subject monitoring, withdrawal criteria, and follow-up procedures.

Subjects will be monitored for side effects and dosage levels will be adjusted if the subject experiences side effects from furosemide. Subjects will not receive additional furosemide if side effects are deemed significant. Subjects will be allowed to withdraw from the study at any time without consequence. If new information about the study becomes available, subjects will be informed and re-consented if applicable.

4. Potential benefit(s) to the subject

Describe any potential medical benefit(s) for subject participation. State if participation results in no benefit to the subject.

The direct medical benefits to the subject for participating in the study include acute control of severe hypertension, which reduces the risk of stroke, placental abruption, hypertensive encephalopathy, and myocardial infarction. An additional benefit may include prolongation of pregnancy at critical gestational ages which may reduce the risks of prematurity which includes respiratory distress, intraventricular hemorrhage, necrotizing enterocolitis, and metabolic and thermic dysregulation.

5. Alternative to participation

Describe any alternative therapies or courses of action available to the subject if they decide not to participate in the study.

Should a subject decide not to participate in the study, they will receive the standard of care for severe hypertension, which typically includes IV labetalol, IV hydralazine, or oral immediate-release nifedipine. However, furosemide is an adjunct that may be administered to the patient per the primary clinician's decision, unrelated to the study.

Section V: Subject Identification, Recruitment and Consent/Assent (If you are requesting a waiver of consent this section can be deleted)

Method of subject identification and recruitment
 Describe how subjects will be identified and recruited. Include steps to minimize
 undue influence if recruitment includes an investigator's students, employees,
 and/or patients.

Contact will be initiated in person at the time of severe range blood pressure and meeting inclusion criteria by the antepartum care provider. If eligible, individuals who are involved in the study and identified as key study personnel will provide information about the study to the subject and if the subject is interested will proceed with obtaining informed consent. Subjects will be informed of the voluntary nature of the study and informed of alternative treatment options.

2. Consent process

Version 2

Protocol Number I

List study team members authorized to obtain consent and describe the process of informed consent.

Informed consent will be primarily conducted by the sub-investigators, principal investigator, and trained residents and fellows who have completed the necessary training for research clearance. The subject will be approached with study information as close to the time at which she meets inclusion criteria, which in many cases will be at the time of admission. If the study participant is not ready to make a decision regarding their participation at the time of informed consent, then the study personnel will return later that day or the next. The informed consent process will consist of reviewing the informed consent documents and asking the subject a series of questions to ensure comprehension (see subject/representative comprehension below).

3. Subject capacity (if applicable)

Describe how capacity will be assessed and by whom. State the anticipated degree of impairment relative to the subject's ability to consent.

Capacity will be assessed by the admitting provider at the time of the admission history and physical by directed clinical interview and exam. This includes the ability to understand information about treatment; the ability to appreciate how that information applies to their situation; the ability to reason with that information; and the ability to make a choice and express it. We anticipate there to be no degree of impairment relative to the subject's ability to consent.

4. Subject/Representative comprehension

Describe how it will be determined that the subject /representative understood the information presented during the informed consent process. If children or decisionally impaired adults will participate, include a plan to assess comprehension during the assent process.

To determine comprehension of the informed consent, subjects will be asked a series of questions. These include:

- 1. Can you briefly recount the purpose of the study and your involvement?
- 2. What is your understanding of your decision to participate in the study, to decline participation, or to discontinue participation after being initially involvement and how this impacts the care you receive?
- 3. In case you have further questions about the study or your involvement, are you aware that you may contact the investigators?

5. **Documentation of consent**

If not addressed in the process of consent section, explain how consent will be documented and where documentation will be stored.

Consent will be documented on the Hawai'i Pacific Health Research Institute IRBapproved informed consent form and by the subinvestigator's password-protected electronic log. Paper documentation will be stored by the subinvestigator in a locked-file

Version 2

Protocol Number I

cabinet and electronic documentation will be stored on a password-protected computer. A copy of the signed consent form will be provided to the subject and will be scanned into the electronic medical record.

6. Costs to the subject

There will be no costs incurred by the subject as a result of participating in the study as this is part of global inpatient pregnancy care and the medications in this study are commonly used in the inpatient setting for the aforementioned medical indications.

7. Payment for participation

There will be no payment for participation in this study.

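### Baseline systolic pressure is used inconsistently and is not a covariate in the primary comparison; adjusting for a pre-named baseline reading would settle the analysis at almost no cost

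*Combined protocol and SAP*

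**What the plan says.** - **Objective (Section I.1).** The question is whether furosemide is "associated with a reduction in mean systolic blood pressure from baseline".
- **Eligibility (Section II.3).** The criterion is "Subjects with persistent (on repeat BP check 15 min apart) severe range blood pressure recordings", with SBP ≥160 or DBP ≥110 and pulse pressure above 60 mmHg. Each eligible woman should therefore have at least two qualifying readings.
- **Baseline (Section III.1, Study Procedures, step 3).** "Patient develops severe range BP (SBP>160 and/or DBP>110) with increased pulse pressure (>60mmHg). This will be considered baseline BP". The step does not mention the repeat check, and does not say whether the first reading, the repeat or their mean supplies the value.
- **Primary outcome and test (Section III.2).** "The primary outcome variable is reduction in mean systolic BP during the 1-hour period after drug administration". Readings at 15, 30, 45 and 60 minutes are averaged. "This study will use a two-sided t-test with the null hypothesis set at the standard significance level".
- **Next paragraph of III.2.** "Change in average BP from baseline will be tested comparing the group receiving furosemide and the group receiving placebo using Mann-Whitney U".
- **Adjusted analysis.** "Multivariate regression will be used to adjust for potential confounders, such as maternal age, BMI, diabetes, baseline BP", and the list goes on to "antihypertensive chosen by the primary obstetrician, number of doses of antihypertensive, and gestational age".
- **Power paragraph of III.2.** SD 20 mmHg, difference 15 mmHg, 28 per arm analysed and 35 per arm enrolled. The paragraph ends by leaving the test to a normality check after data collection. It does not say whether 20 mmHg is the SD of the 1-hour mean or of the change.

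**The concern.** Two things are unsettled in the primary comparison. The outcome can be read as the 1-hour mean or as its change from baseline, and the test as a t-test or a Mann-Whitney test. These combinations can fall on different sides of p = 0.05 in the same data. Under no reading is baseline a covariate in the primary test, although it is measured before randomisation and should predict the outcome to some extent.

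The planned regression does not fill the gap. Its covariate list is open-ended. It also includes the number of antihypertensive doses, and any dose given after study drug may depend on whether furosemide has already lowered the pressure. Adjusting for such a variable changes the question from the total effect of adding furosemide to something harder to interpret.

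At stake are a clearly fixed primary result and a small amount of precision. The validity of the randomised comparison is not in doubt.

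**Working it through.** **1. The plan's own figure.** With SD 20, difference 15, two-sided 0.05 and 80% power:

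n per arm = 2 × [(1.960 + 0.842) × 20 / 15]² = 27.9, so 28.

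Enrolment: 28 / 0.80 = 35 per arm, 70 in total. Both figures reproduce. Power at 28 per arm is 80.1% by the normal approximation and 78.7% by the noncentral t distribution.

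**2. Why the covariate removes the mean-or-change ambiguity.** Write Y for the 1-hour mean, B for baseline and A for arm. If Y = a + dA + bB + error, then Y − B = a + dA + (b − 1)B + error. Only the coefficient of B changes. The arm estimate d, its standard error and its p-value are identical.

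**3. Size of the gain by formula.** Take 20 mmHg as the SD of the 1-hour mean. The residual SD is 20 × √(1 − r²), where r is the baseline-to-outcome correlation. The documents give no r, so it is an assumed range.

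| r | Residual SD | Power, normal | Power, noncentral t (53 df) |
|---|---|---|---|
| 0 | 20.00 | 80.1% | 78.7% |
| 0.2 | 19.60 | 81.7% | 80.3% |
| 0.3 | 19.08 | 83.7% | 82.3% |
| 0.5 | 17.32 | 90.0% | 88.9% |

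Entry requires high readings, which narrows the spread of B and lowers r. In simulations with selection at SBP ≥160, r was about 0.13 to 0.35, so the last row is optimistic.

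**4. Size of the gain by simulation.** Assumptions, none given in the documents: true SBP mean 150 or 165 with SD 12; independent, normal reading error of SD 6 to 10; both qualifying readings ≥160; outcome the mean of four readings; SD of change from one reading set to 20; 28 per arm; true difference 15 mmHg. The covariate is the mean of the two qualifying readings.

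| Analysis | Fall unrelated to baseline | Higher pressures fall more (slope 0.5) |
|---|---|---|
| Linear model with baseline | 79.4–81.7% | 80.0–84.6% |
| t-test, change from one reading | 78.3–79.2% | 78.4–79.0% |
| t-test, post-dose mean | 75.1–79.1% | 80.0–84.2% |
| Mann-Whitney, change from one reading | 75.7–76.4% | 75.6–76.4% |

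Compared within the same scenario, the gain over the t-test on change is 0.3 to 3.1 points in the first column and 1.5 to 6.2 in the second. Over the t-test on the post-dose mean it runs from near zero to about 5. The model was never more than 0.2 points below any comparator here, and its type I error was 4.9 to 5.3%. Its residual SD was 18.3 to 19.7, so against an SD of 20 the saving is 28 × [1 − (19.7/20)²] ≈ 1 to 28 × [1 − (18.3/20)²] ≈ 5 women per arm.

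**5. Limit of step 4.** The advantage over Mann-Whitney depends on roughly normal outcomes. In two runs with heavy-tailed (Laplace) outcomes, Mann-Whitney on change had 81.8% and 91.8% power, against 79.9% and 85.6% for the linear model.

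**6. Which reading.** If errors 15 minutes apart are correlated (assumed 0.5 to 0.7), using the mean of both readings as covariate is within 0.3 points of using the repeat alone. Switching from the first to the repeat reading in a change-score analysis moves the estimate by a median of 1.2 to 2.1 mmHg. Mixing the two at random leaves type I error at 4.9 to 5.3%.

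**7. How often the planned tests disagree.** With a true difference of 15 mmHg, the t-test on the post-dose mean and Mann-Whitney on change fell on opposite sides of 0.05 in 10 to 15% of simulated trials. When both tests used the same change score, disagreement was 5.5 to 5.8%.

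**8. Threshold wording.** Step 3 writes >160 and >110, while Section II.3 and the opening of III.1 write ≥. DBP of at least 110 with pulse pressure above 60 implies SBP above 170, so the sign matters only at SBP of exactly 160.

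**The case against.** The strongest reply is that baseline is already in the plan. The objective speaks of reduction from baseline, the outcome is called a reduction, the Mann-Whitney test uses change, and the regression lists baseline pressure. That is right, and a reader who infers that the primary comparison ignores baseline goes too far. Baseline enters by subtraction under some readings. What stands is that its use is inconsistent and that it is not a covariate in the primary test.

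Other replies also have force:

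- **Missing detail only.** A reader might infer that the undefined reading biases the comparison or inflates type I error. It does not: both readings precede randomisation and the trial is double-blind. Error rose to 6.5–8.0% only when the most favourable of first, repeat or mean was picked after unblinding, and nothing in the protocol suggests that.
- **Power reserve.** A reader might infer that 28 per arm leaves no margin. The plan enrols 35 per arm, specifies intention-to-treat and measures the outcome within an hour of dosing. If all 70 contribute, noncentral-t power is 87.1%.
- **Averaging.** The case for the mean of two readings rests on independent errors. With correlated errors the repeat reading does as well.
- **The test rule.** The plan does give a rule, the normality check. But that rule is data-driven and does not say whether the outcome is the mean or the change.

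**Conclusion.** The point holds as a recommendation for a better primary analysis. The plan leaves outcome form and test unsettled, and its only baseline-adjusted analysis includes a variable that treatment may affect. One linear model with a pre-named baseline resolves the choice between mean and change.

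The efficiency gain is modest: roughly 0.3 to 6 power points over a t-test on change from one reading, and near zero to about 5 over a t-test on the post-dose mean, at 28 per arm. These figures depend on assumed SBP distributions, reading error and approximate normality. The documents fix none of these, nor the correlation. Larger gains, such as 90% power at r = 0.5, are possible by formula but unlikely given selection on severe readings. The documents do not support a claim that the planned comparison is biased or that the sample size is wrong.

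**What to change.** 1. State one primary between-arm analysis: a linear model of mean 1-hour post-dose SBP (or its change; the arm estimate is identical) on arm, with baseline SBP as covariate. Remove the choice of primary test by normality check.
2. Name the baseline in advance as a fixed pre-dose qualifying reading: the repeat reading, or the mean of the two where both come from the dosing episode.
3. Keep Mann-Whitney on change from that baseline as a sensitivity analysis, which covers the heavy-tailed case.
4. Keep the wider regression as secondary, with a closed covariate list that excludes antihypertensive doses given after study drug.
5. Reconcile step 3 with Section II.3 and the opening of Section III.1 on the threshold sign and the repeat check. Which threshold applies is for the investigators to decide.

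The cost is a few sentences, one field on the data form and one degree of freedom (53 instead of 54). No new measurement is needed if the repeat check is made in the dosing episode. Since step 3 does not mention that check, the text should say so.
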